### **2.3.2. Anticipated Risks**

As with all injectable vaccines, immediate systemic allergic reactions to vaccination can occur. These reactions are very rare and are estimated to occur once per 450,000 vaccinations for vaccines that do not contain allergens such as gelatin or egg protein ([Zent et al 2002](#)). As a precautionary measure, all participants will remain under observation at the study site for at least 60 minutes after vaccination.

Vasovagal syncope (fainting) can occur before or after any vaccination, is usually triggered by the pain or anxiety caused by the injection, and is not related to the substance injected. Therefore, it is important that standard precautions and procedures will be followed to avoid injury from fainting.

IM vaccination commonly precipitates a transient and self-limiting local inflammatory reaction. This typically includes injection site pain, erythema (redness), or swelling/induration (hardness).

In the current, ongoing Phase 1 study of mRNA-1647, dose levels of 30 µg, 90 µg, 180 µg and 300 µg have been administered to healthy adults. A preliminary analysis of safety through one month after the final vaccination for all 4 dose levels was performed. The majority of local and systemic adverse reactions (ARs) within 7 days following vaccination were of mild or moderate severity and brief in duration. The most common local and systemic ARs observed have been injection site pain, myalgia, headache, chills, and fatigue. The majority of reported unsolicited adverse events (AEs) were not considered to be related to study vaccine by site Investigators.

A Phase 1 study with a similar mRNA-based vaccine, mRNA-1653, targeting human metapneumovirus (hMPV) and parainfluenza virus type 3 (PIV3) is ongoing in healthy adults with doses ranging from 25 µg to 300 µg administered as a 2-dose series. An interim analysis was performed through 1 month following the second vaccination. The study vaccine was generally well-tolerated. Within 7 days following vaccination, the most common local reactogenicity event was injection site pain and the most common systemic reactogenicity events were headache, fatigue and myalgia which appeared to increase with dose level after first vaccination.

Further details are provided in the current IB.

### **2.3.3. Overall Benefit/Risk Conclusion**

mRNA-1647 is currently in a very early stage of investigation and no vaccine efficacy has been demonstrated thus far. Taking into account the measures taken to minimize the risk to individuals participating in this study, the potential risks to the participants are justified by the potential benefits linked to the development of mRNA-1647.

### **3. OBJECTIVES AND ENDPOINTS**

#### **3.1. Objectives**

##### **3.1.1. Primary Objectives**

The primary objectives of the study are as follows:

- To evaluate the safety of different dose levels of mRNA-1647 vaccine administered in a 3-vaccination (0, 2, 6-month) schedule.
- To evaluate neutralizing anti-CMV antibody responses against fibroblast and epithelial cell infection following vaccination with mRNA-1647 at different dose levels administered in a 3-vaccination (0, 2, 6-month) schedule.

##### **3.1.2. Secondary Objectives**

The secondary objectives of the study are as follows:

- To evaluate antigen-specific antibody responses following vaccination with mRNA-1647 at different dose levels in a 3-vaccination schedule.
- To evaluate the immunogenicity of mRNA-1647 by CMV serostatus at enrollment.

##### **3.1.3. Exploratory Objectives**

The exploratory objectives of the study are as follows:

- To evaluate cell-mediated immune responses following vaccination with mRNA-1647 at different dose levels.
- In CMV-seropositive participants, to assess possible effects of immunologic response following vaccination with mRNA-1647 compared to placebo.

#### **3.2. Endpoints**

##### **3.2.1. Primary Endpoints**

- Solicited local and systemic ARs through 7 days after each vaccination.
- Unsolicited AEs through 28 days after each vaccination.
- Medically-attended adverse events (MAAEs) through 6 months after the last vaccination, and serious adverse events (SAEs) throughout the entire study period.

- Geometric mean titer (GMT) of serum neutralizing anti-CMV antibodies against epithelial cell infection and against fibroblast infection, and associated geometric mean ratio (GMR) of post-baseline/baseline titers at each timepoint.
- Proportion of participants with  $\geq 2$ -fold, 3-fold, and 4-fold increases in nAb over baseline against epithelial cell infection and against fibroblast infection at each timepoint.

### **3.2.2. Secondary Endpoints**

- GMT of anti-gB specific IgG and anti-Pentamer specific IgG as measured by enzyme-linked immunosorbent assay (ELISA), and associated GMR of post-baseline/baseline titers at each timepoint.
- GMT, GMR, and proportion of participants with  $\geq 2$ -fold, 3-fold, and 4-fold increases over baseline of serum nAb against epithelial cell infection and against fibroblast infection at each timepoint, and GMT and GMR of antigen-specific IgG (ELISA) at each timepoint, in the CMV-seropositive group and in the CMV-seronegative group.

### **3.2.3. Exploratory Endpoints**

- gB- and Pentamer-specific interferon (IFN)- $\gamma$ -secreting T-cells as measured by enzyme-linked immunospot (ELISpot) assay.
- Exploratory assays to assess for anti-CMV immunologic response or for primary CMV infection may be performed at the discretion of the Sponsor.

## 4. STUDY DESIGN

### 4.1. Overall Design

This is a Phase 2, randomized, placebo-controlled, observer-blind, dose-finding trial enrolling healthy participants 18-40 years of age. The schematic of the study design is presented in [Figure 1](#) in [Section 1.2](#).

CMV-seronegative and CMV-seropositive groups will be enrolled at the same time. Randomization will be stratified by CMV serostatus (via an Interactive Response Technology [IRT]) in a sequential manner into 3 different dose levels **CCI** in Part 1 and the **CCI** dose level in Part 2. At each dose level, participants will be randomized in 3:1 ratio to either mRNA-1647 vaccine or placebo, administered in a 3-vaccination (0, 2, 6-month) schedule.

#### Treatment Arms

##### Part 1 CMV-seronegative Group (males and females aged 18-40 years)

- Approximately 60 participants randomized 3:1 to receive either **CCI** of mRNA-1647 vaccine or placebo in a 0, 2, 6-month schedule
- Approximately 60 participants randomized 3:1 to receive either **CCI** of mRNA-1647 vaccine or placebo in a 0, 2, 6-month schedule
- Approximately 60 participants randomized 3:1 to receive either **CCI** of mRNA-1647 vaccine or placebo in a 0, 2, 6-month schedule

##### Part 1 CMV-seropositive Group (males and females aged 18-40 years)

- Approximately 24 participants randomized 3:1 to receive either **CCI** of mRNA-1647 vaccine or placebo in a 0, 2, 6-month schedule
- Approximately 24 participants randomized 3:1 to receive either **CCI** of mRNA-1647 vaccine or placebo in a 0, 2, 6-month schedule
- Approximately 24 participants randomized 3:1 to receive either **CCI** of mRNA-1647 vaccine or placebo in a 0, 2, 6-month schedule

##### Part 2 CMV-seronegative Group (females aged 18-40 years)

- Approximately 80 participants randomized 3:1 to receive either **CCI** of mRNA-1647 vaccine or placebo in a 0, 2, 6-month schedule

##### Part 2 CMV-seropositive Group (females aged 18-40 years)

- Approximately 120 participants randomized 3:1 to receive either **CCI** of mRNA-1647 vaccine or placebo in a 0, 2, 6-month schedule

#### 4.1.1. Screening Period

The Screening of each participant will occur during the first visit at the clinic. In Part 1, screening may occur up to 28 days prior to Visit Day 1. For Part 2, screening may occur up to 28 days prior

to Visit Day 1 for CMV-seronegative participants and may occur up to 42 days for CMV-seropositive participants.

Based on prior approval from the Sponsor, the Screening visit may be performed across 2 separate clinic visits.

#### **4.1.2. Treatment Period**

All participants will receive vaccinations at Visits Day 1, Day 56, and Day 168.

#### **4.1.3. Follow-up Period**

All participants will be followed for safety for a minimum of 6 months after the last vaccination for MAAEs and up to 12 months after last vaccination for SAEs (refer to [Table 1](#) and to [Appendix 2](#)).

Participants who withdraw from further vaccinations after either the first or second vaccination but do not withdraw consent will be followed for safety as noted above, and will provide blood samples for immunogenicity at specified timepoints (refer to [Table 6](#) and [Table 7](#) in [Appendix 2](#)).

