-  All scheduled study visits should be completed within the defined visit window. Timing of Dose 3 is calculated in relation to Dose 1 (Day 1) and should not shift later than 167 days ( $\pm 7$  days) after Day 1; succeeding follow-up visits (Visits 10-17) are scheduled in relation to Dose 3. In the event the participant is not able to come on site for a clinic visit as a result of the COVID-19 pandemic (self-quarantine or disruption of clinical site activities following business continuity plans and/or local government mandates for “stay at home” or “shelter in place”), a safety call to the participant should be made in place of the clinic visit. The safety call should encompass all scheduled visit assessments that can be completed remotely, such as assessment for AEs and concomitant medications (eg, as defined in scheduled safety calls at Visits 12-15). Home visits will be permitted for all non-dosing visits in the event a participant cannot make it to the clinic as a result of the COVID-19 pandemic. Home visits must be permitted by the site IRB and the participant via informed consent and have prior approval from the Sponsor (or its designee).

-  In the event the visit for Dose 2 is disrupted and cannot be completed at Day 56  $\pm$  7 days as a result of the COVID-19 pandemic (COVID-19 vaccination under the FDA EUA or FDA approval, self-quarantine or disruption of clinical site activities following business continuity plans and/or local government mandates for “stay at home” or “shelter in place”), the window may be extended to Day 56 + 56 days (i.e., to 4 -months). When the extended window is utilized, the Day 84 visit is to be completed at 28 (-7 to +21) days after Dose 2 and monthly safety calls should occur every 28 days  $\pm$  7 days until the Month 6 visit (Day 168) for Dose 3. Dose 3 timing should continue to be based on Dose 1 and should not be adjusted if Dose 2 occurs in the extended dosing window (Dose 3 should not shift later than 167 days [ $\pm$  7 days] after Day 1); succeeding follow-up visits (Visits 10-17) are scheduled in relation to Dose 3.
-  Only documentation of COVID-19 vaccine is required.
-  Upon completion of final study procedures, including the final assessment and recording of MAAEs and SAEs, the participant’s treatment assignment may be unblinded via the IRT system.

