At each vaccination visit, participants will be instructed (Visit Day 1) or reminded (Visit Day 56 and Day 168) on thermometer usage to measure body temperature, ruler usage to measure injection site erythema and swelling/induration (hardness), and self-assessment for localized axillary swelling or tenderness ipsilateral to the vaccination arm. Participants will record body temperature, any solicited local (injection site) and systemic ARs, and whether any medications were taken to prevent or treat pain or fever starting on the day of each vaccination visit, at approximately 1 hour post vaccination under supervision of the clinical site staff to ensure successful entry of assessments. The site staff will perform any re-training as necessary. Thereafter, the participant will be instructed to complete the eDiary later that day, preferably in the evening and at the same time each day on the 6 subsequent days post vaccination. If any solicited ARs are ongoing at 7 days post vaccination, the participant will be prompted to capture the ongoing solicited ARs in the eDiary until it is no longer reported. Adverse reactions recorded in eDiaries beyond Day 7 should be reviewed either via phone call or at the following study visit.

Site personnel will review completed eDiary assessments during discussion with the participants on Day 8, Day 29, Day 56, Day 63, Day 84, Day 175, and Day 196, as applicable.

Additionally, delegated site staff will interview the participant to assess the occurrence of any unsolicited AEs, SAEs and medications taken. Unsolicited AEs will be captured from Day 1 through 28 days after each dose, and MAAEs from Day 1 to Day 336. SAEs will be captured from time of informed consent to the end of the study. The Investigator or designated site staff will transcribe the collected information into the eCRF.

The only source documents allowed for solicited systemic and local ARs (including body temperature measurements) will be the eDiary. The following additional rules apply to documentation of safety information collected using eDiary:

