-  eDiary entries will be recorded by the participant at approximately 1 hour after vaccination while at the clinic with instruction provided by study staff. Study participants will continue to record in the diary each day after they leave the clinic, preferably in the evening, on the day of vaccination and for 6 days following vaccination. Any solicited AR that is ongoing beyond Day 7 will be reported until resolution. Adverse reactions recorded in eDiaries beyond Day 7 should be reviewed either via phone call or at the following study visit.
-  Trained study personnel will call all participants to collect information relating to any MAAEs, AEs leading to study discontinuation, SAEs, information on concomitant medications associated with those events, and any vaccinations.
-  All non-study vaccinations administered during the period starting  $\leq 28$  days before the first dose of study vaccine and all concomitant medications and non-study vaccinations through 28 days after each vaccination will be recorded; COVID-19 vaccination (regardless of type of vaccine) will be recorded anytime from Day 1 through the End of the Study (Day 420); all concomitant medications relevant to or for the treatment of an SAE will be recorded from Screening through the End of Study (Day 420), and all concomitant medications relevant to or for the treatment of a MAAE will be recorded from Visit 1 (Day 1) through Day 252.
-  Blood for exploratory cell-mediated immunogenicity will be collected for a subset of up to 16 participants (approximately 8 CMV-seropositive and 8 CMV-seronegative) for each dose level. The Sponsor will allocate clinical sites to enroll participants in this subset. Participants engaging in blood sampling for cell-mediated immunogenicity should be advised to refrain from blood donation through the vaccination period (Day 1 through Month 7).
-  All scheduled study visits should be completed within the defined visit window. In the event the participant is not able to come on site for a clinic visit as a result of the COVID-19 pandemic (COVID-19 vaccination under the FDA EUA or FDA approval, self-quarantine or disruption of clinical site activities following business continuity plans and/or local government mandates for “stay at home” or “shelter in place”), a safety call to the participant should be made in place of the clinic visit. The safety

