call should encompass all scheduled visit assessments that can be completed remotely, such as assessment for AEs and concomitant medications (eg, as defined in scheduled safety calls at Visits 12-15). Home visits will be permitted for all non-dosing visits in the event a participant cannot make it to the clinic as a result of the COVID-19 pandemic. Home visits must be permitted by the site IRB and the participant via informed consent and have prior approval from the Sponsor (or its designee).

-  In the event the visit for Dose 2 is disrupted and cannot be completed at Day 56  $\pm$  7 days as a result of the COVID-19 pandemic (COVID19 vaccination under the FDA EUA or FDA approval, self-quarantine or disruption of clinical site activities following business continuity plans and/or local government mandates for “stay at home” or “shelter in place”), the window may be extended to Day 56 + 56 days (ie, to 4 months). When the extended window is utilized, the Day 84 visit is to be completed at 28 (-7 to +21) days after Dose 2 and monthly safety calls should occur every 28 days  $\pm$  7 days until the Month 6 visit (Day 168).
-  Only documentation of the COVID-19 vaccine is required for Visit 7 (Day 110) through Visit 12 (Day 420).
-  Upon completion of final study procedures, including the final assessment and recording of MAAEs and SAEs, the participant’s treatment assignment may be unblinded via the IRT system.

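### For participants with a late Dose 2 and no Dose 3, the protocol contradicts itself on when MAAE follow-up ends: by study day it can be as short as 140 days, by days since vaccination it is 196

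*Protocol*

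**What the plan says.** **The requirement.** Section 4.1.3 says: "All participants will be followed for safety for a minimum of 6 months after the last vaccination for MAAEs". Its second paragraph applies this to people who stop vaccination after the first or second dose. Section 3.2.1 lists as a primary endpoint: "Medically-attended adverse events (MAAEs) through 6 months after the last vaccination".

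**Table 6 (two doses only), read by study day.** Footnote 13 covers a Dose 2 disrupted by the pandemic: "the window may be extended to Day 56 + 56 days (ie, to 4 months", that is, Day 112. It then re-times one visit, "the Day 84 visit is to be completed at 28 (-7 to +21) days after Dose 2", and asks for monthly calls up to Day 168. It says nothing about moving the visits labelled D252 and D420. Footnote 10 says: "all concomitant medications relevant to or for the treatment of a MAAE will be recorded from Visit 1 (Day 1) through Day 252". The MAAE row is marked at the D252 visit and blank at D420.

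**Table 6, read by days since vaccination.** A header row lists the D252 and D420 visits as 196 and 364 days since the most recent vaccination. It names only the M6/D168 visit as based on Day 1.

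**Elsewhere in the protocol.** Section 7.1 places the immunogenicity samples of these participants at timepoints following their last dose and refers to Table 6. Section 8.9.1.3 collects "MAAEs from Day 1 to Day 336" with no exception for people who stop early. The synopsis gives Day 336 with six months from the last dose as an alternative. For participants who receive Dose 3, Table 1 footnote 13 is explicit: "succeeding follow-up visits (Visits 10-17) are scheduled in relation to Dose 3".

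**The concern.** When Dose 2 is on time, all the Table 6 statements agree. When the extended window is used and Dose 3 is not given, they separate. Table 1 has a sentence tying later visits to the last dose; Table 6 has no counterpart, although its footnote 13 otherwise follows Table 1 footnote 14 closely. A site that works from the day labels could close MAAE recording before six months have passed, while following a schedule and a window that the protocol itself provides.

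At stake is the completeness of a primary safety endpoint in people whose vaccination was disrupted and then stopped. SAP Section 6.3.1 bases percentages on the Safety Set and states no adjustment for shorter MAAE observation. SAP Section 6.2.1 does summarise study duration since the second vaccination, but that runs to study completion or discontinuation. It would not show an earlier end to MAAE recording.

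**Working it through.** **Inputs.** Dose 2 on schedule: Day 56. Latest extended Dose 2: 56 + 56 = Day 112 (Table 6 footnote 13). Last visit marked for MAAEs in Table 6: Day 252 ± 7. Last visit marked for MAAEs in Table 1: Day 336, with Dose 3 at Day 168.

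**Reproducing the protocol's own figures.** Table 6: 252 − 56 = 196 and 420 − 56 = 364, both as printed. Table 1: 336 − 168 = 168, as printed. The protocol's working value for six months is therefore 168 days. (Table 7, for one dose, gives 168 − 1 = 167.)

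**MAAE follow-up after Dose 2 when Dose 3 is not given.** For Dose 2 on day d, the study-day reading gives 252 − d, or 245 − d if the visit is 7 days early. The days-since-vaccination reading gives 196 for every d.

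| Dose 2 day | 252 − d | 245 − d | 196-day row |
|---|---|---|---|
| 56 (on time) | 196 | 189 | 196 |
| 63 (end of normal window) | 189 | 182 | 196 |
| 84 | 168 | 161 | 196 |
| 85 | 167 | 160 | 196 |
| 112 (latest) | 140 | 133 | 196 |

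**Size under the study-day reading.** At Day 112 the shortfall is 168 − 140 = 28 days (28/168 = 17%), or 168 − 133 = 35 days with an early visit. The nominal figure first drops below 168 when Dose 2 is on Day 85, since 252 − 84 = 168. With the visit 7 days early, it first drops below 168 at Day 78 (245 − 78 = 167).

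**Sensitivity to the meaning of six months.** If six months is taken as 182 days (an assumption, not a protocol figure), the Day 112 shortfall is 182 − 140 = 42 days. The nominal threshold is then Day 71 (252 − 71 = 181).

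**The other readings at Day 112.** By the 196-day row, the visit labelled D252 falls on 112 + 196 = Day 308. By Section 8.9.1.3, follow-up is 336 − 112 = 224 days. Both exceed 168.

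**The case against.** The best reply is that Table 6 already has an anchor. Its header row counts from the most recent vaccination and excepts only M6/D168, so the D252 visit should move with Dose 2. Section 7.1 supports this, although it speaks of blood samples. Day numbers in this protocol also serve as visit names: Table 1 footnote 11 still says Day 336 and Day 504 although those visits follow Dose 3, and Table 6 footnote 13 moves the Day 84 visit without renaming it. Footnote 10 strictly concerns concomitant medications given for a MAAE, not the recording of the MAAE. SAP Appendix B accepts a two-dose antibody sample at either time, because its window for the Day 252 target runs from Day 168 to Day 335.

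Much of this stands, and it rules out calling Day 252 a settled cut-off. It does not remove the conflict. The figure of 196 is simply the on-time value, 252 − 56. If the row alone governed timing, footnote 13 would not have needed to re-time the Day 84 visit, since the row already shows 28 days there. Table 1 has the same kind of row, yet an explicit sentence was added for Dose 3. The Day 336 statements do not settle the question for Table 6 either: they disagree with its Day 252 and are a third version of the end point.

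**Conclusion.** The point holds as an internal contradiction. For a participant with Dose 2 after Day 84 and no Dose 3, one reading of Table 6 gives less than the stated MAAE minimum (140 nominal days at the extreme, 133 with the visit window) and another meets it with 196 days. This assumes six months means the 168 days of Table 1.

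A reader might infer four stronger conclusions that the documents do not support:

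- **That recording stops at a fixed Day 252.** The 196-day row, Section 4.1.3, Section 8.9.1.3 and the synopsis all point to longer recording.
- **That the endpoint is unobserved for everyone in the extended window.** Dose 2 on Days 64 to 84 still gives at least 168 nominal days. At Day 112, 140 of the 168 days are covered, so the endpoint is incompletely observed.
- **That SAE follow-up also falls short.** By study day it would be 420 − 112 = 308 days, but Section 4.1.3 sets 12 months for SAEs as an upper limit, so no minimum is breached.
- **That no contact is planned between Day 168 and Day 252.** Table 6 has four call visits (7 to 10, M4-7), and its offset of 140 days corresponds to Day 196. Only a day label is missing, which may be a loss in reading the PDF.

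The documents do not say how many participants had a late Dose 2 and no Dose 3. The number is probably small, so the effect on the MAAE summaries cannot be sized and is likely limited.

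**What to change.** **Protocol.** Reconcile the Table 6 visit days, its 196/364-day row and footnotes 10 and 13 with Sections 3.2.1, 4.1.3, 7.1 and 8.9.1.3 and the synopsis. One stated anchor should apply after a late Dose 2, and the protocol's own six-month MAAE minimum should be met. The choice of anchor is the sponsor's. Table 1 footnote 13 shows how explicitly it can be stated. The cost is a few lines of wording.

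**Final analysis.** Count the participants with Dose 2 after Day 84 and no Dose 3, by serostatus and vaccination group. Report their MAAE observation time from the last dose to the last MAAE assessment, and say which anchor the sites applied. This needs only dosing and visit dates and one short table or listing. SAP version 5.0 precedes the final database lock, so it can be added without new data collection, and it is useful even if follow-up of these participants has already ended.
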